The safety profile of avapritinib has been well characterised in patients with GIST and adverse events associated with avapritinib treatment can be managed with adherence to product labeling. As of 09 March 2020, the safety database included a total of 585 patients with GIST (all doses), of which 550 patients received avapritinib at a starting dose of 300 mg or 400 mg. This includes 250 patients in the Phase I study BLU-285-1101 who received treatment with avapritinib, and 473 patients in the Phase III study BLU-285-1303 that compared avapritinib versus regorafenib in patients with GIST beyond second line, including 239 patients who received avapritinib and 96 patients who received regorafenib and then crossed over to receive avapritinib treatment upon disease progression. Safety data from study BLU-285-1101 (DCO 09 March 2020) showed that all patients except for one (>99%) reported adverse events (AEs), where 80% of patients reported an AE \geq Grade 3 (13% fatal Grade 5 AEs), 65% reported serious AEs (SAEs) and 27% reported AEs that led to permanent discontinuation of study drug. The safety analysis from the study BLU-285-1303 was consistent with the safety results reported from BLU-285-1101 and no new safety signals were identified. Overall, 99% of the patients in the avapritinib treatment arm reported any AEs, where 75% of patients reported \geq Grade 3 AEs (4% Grade 5 AEs), 41% SAEs, and 13% AEs that lead to treatment discontinuation. Based on the pooled analysis of studies BLU-285-1101 and BLU-285-1303, the most frequently reported treatment related AEs of any grade during treatment with avapritinib were nausea (45%), fatigue (40%), anaemia (39.6%), periorbital oedema (33%), hyperbilirubinaemia (27%), face oedema (27%), diarrhoea (26%), vomiting (24%), blood bilirubin increased (24%), oedema peripheral (23%), lacrimation increased (22%), decreased appetite (21%) and memory impairment (20%). A total of 20.1% of patients experienced SAEs that were considered treatment-related. Treatment-related SAEs

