The study period for the efficacy analyses is defined as the time from the first dose of avapritinib to the end of follow-up at 24 months, until initiation of second-line treatment or until study discontinuation for any reason; whichever comes first. Survival is an exception and will be ascertained for all patients until study closure, which will occur when the last patient enrolled has been followed for at least 24 months or withdraws from the study for any reason. The analyses to be performed will be:

- Median, 95% CIs and 25th and 75th percentiles using the Kaplan-Meier (KM) method for:
 - OS
 - PFS
 - DoR
 - DoT
- OS rates at select timepoints
- ORR during the study period with 95% CI based on the exact binomial distribution

The following definitions will be used for the above outcomes:

- OS is defined as the time in months from the start of avapritinib treatment to the date of death due to any cause.
- PFS is defined as the time in months from the start of avapritinib treatment to the date of the first documented disease progression by a responsible physician according to mRECIST 1.1 criteria or local standard practice, or death.

- DoT is defined as the time from the date of the first to the date of the last avapritinib dose.
- DoR is defined as the time from the date of the first documented disease response to the date of disease progression.
- ORR is defined as the proportion of patients with a best response during the study period of complete response (CR) or partial response (PR) evaluated by a responsible physician based on mRECIST v1.1 criteria if feasible or to local standard practice.

An interim analysis is planned for an interim study report (data lock point in August 2024, submission interim report in February 2025). Details of the interim analysis will be described in the SAP.

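### Duration of response ends at progression only, while PFS counts death: the same death is a PFS event but not a DoR event, and any such death pushes reported DoR upward

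*Protocol*

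**What the plan says.** All the relevant text is in protocol section 9.7.2, under the analysis of the secondary endpoints.

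- **DoR:** "DoR is defined as the time from the date of the first documented disease response to the date of disease progression". Death is not mentioned.
- **PFS:** runs from the start of treatment to "first documented disease progression by a responsible physician according to mRECIST 1.1 criteria or local standard practice, or death".
- **OS:** "OS is defined as the time in months from the start of avapritinib treatment to the date of death due to any cause".
- **Summary method:** "Median, 95% CIs and 25th and 75th percentiles using the Kaplan-Meier (KM) method for" OS, PFS, DoR and DoT alike.
- **Efficacy window:** from first dose to "the end of follow-up at 24 months, until initiation of second-line treatment or until study discontinuation for any reason; whichever comes first".
- **Deaths:** "Survival is an exception and will be ascertained for all patients until study closure".

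No other section adds death to DoR, gives a censoring rule for it, or plans a competing-risk analysis. Section 9.7 leaves further information to the SAP, including on missing data and on differences in outcome definitions.

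**The concern.** Two time-to-event endpoints in one list, analysed by one method, treat the same death differently. For PFS, death without documented progression is a failure. For DoR it is not an event, and if it is censored the patient is treated as someone who could still progress later.

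The overlap between the two endpoints makes this visible. Section 7.1 reports an ORR of 95% in patients with the D842V mutation in BLU-285-1101, and 100% in the first-line patients (a small group; the section counts 11). If response is similar here, almost everyone in the PFS analysis also enters the DoR analysis. One report would then show nearly the same patients under two event rules, with DoR looking better for a reason unrelated to how long responses last. The study serves a Specific Obligation of the conditional authorisation (section 7.2), so its efficacy durations will be read as evidence on benefit-risk.

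**Working it through.** The protocol states no DoR figure, so there is nothing to reproduce. The check is of direction first, then of size.

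**1. Direction.** Take the same responders, with the same times from response. The Kaplan-Meier curve is a product of factors 1 - (events / number at risk).

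- Progression-only: a death without progression contributes a factor of 1 and leaves the risk set.
- Progression or death: the same death contributes a factor below 1 and leaves the risk set at the same time.

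The risk sets are identical, so the progression-only curve is never below the other, and it lies above it from the first such death onward. This needs no assumption about hazards.

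**2. Size.** Inputs:

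- Hazard of progression after response, h_p: not given.
- Hazard of death without progression, h_d: not given.
- s = h_d / (h_p + h_d), the share of first events that are deaths without progression: not given; assumed 5% to 30%.
- Median DoR under the progression-only rule: not given; 24 and 36 months assumed for illustration.

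With constant hazards:

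- Median, death censored = ln 2 / h_p
- Median, death counted = ln 2 / (h_p + h_d)
- Ratio = (h_p + h_d) / h_p = 1/(1-s)

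The 25th percentile is ln(4/3) divided by the same hazard, that is 0.415 times the median, so it scales by the same ratio. Months with death counted are the progression-only value times (1-s):

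| s | Inflation 1/(1-s) | Median, from 24 | Median, from 36 | 25th percentile, from 10.0 | 25th percentile, from 14.9 |
|---|---|---|---|---|---|
| 0% | 1.00 | 24.0 | 36.0 | 10.0 | 14.9 |
| 5% | 1.05 | 22.8 | 34.2 | 9.5 | 14.2 |
| 10% | 1.11 | 21.6 | 32.4 | 9.0 | 13.4 |
| 20% | 1.25 | 19.2 | 28.8 | 8.0 | 12.0 |
| 30% | 1.43 | 16.8 | 25.2 | 7.0 | 10.5 |

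The starting 25th percentiles are 24 x 0.415 = 10.0 and 36 x 0.415 = 14.9 months.

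**3. What would be seen.** Section 9.7.2 ends the efficacy period 24 months after first dose, and DoR starts later, at first response. On that text a DoR of 24 months cannot be observed, so a median that long would not be reached. Sections 9.3 and 9.4 speak of at least 24 months, so some patients may be followed longer. Within the 24-month window, the planned 25th percentile is where the difference is most likely to appear.

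**The case against.** The strongest reply concerns importance. The primary objective is to describe adverse events and deaths. DoR is one of several secondary, descriptive summaries. No test or decision rule uses it, and the sample-size statement in section 9.5 concerns ORR. Deaths are not hidden: PFS and OS count them and the primary objective reports them. All of this stands, and it limits the weight of the point.

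A second reply is that the protocol never says these patients are censored, and the SAP, not available here, may state the handling. The first half is right: censoring is inferred from a progression-only event analysed by Kaplan-Meier. The second half does not remove the problem. The end event is a stated rule, not a detail left open, and a SAP that counted death would contradict it.

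Three stronger readings are tempting, and the protocol does not support them:

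- **Taking s from the background safety data.** A reader might use the figure for BLU-285-1101, "13% fatal Grade 5 AEs". That is a proportion of all treated patients with GIST, not of first events among first-line D842V responders. Section 7.1 also gives 4% for BLU-285-1303. It lists disease progression among the adverse events leading to discontinuation, so some fatal events may have followed progression. Neither figure is an estimate of s.
- **Quoting an inflated median beyond 24 months as the expected result.** The efficacy window in section 9.7.2 would not show it.
- **Calling deaths before documented progression likely.** Visits are planned at least monthly where practical for three months and then every 2-3 months, and progression may be recorded by local practice. Such deaths are possible; nothing in the protocol says how frequent they will be.

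It can also be said that the calculation compares two definitions and does not demonstrate informative censoring. That is correct. The claim is an upward shift relative to progression-or-death and an inconsistency with PFS, and neither depends on showing dependence between death and progression.

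**Conclusion.** The point holds as a moderate definitional error in a secondary endpoint. Section 9.7.2 ends DoR at progression alone and PFS at progression or death, in largely the same patients if response resembles that in BLU-285-1101. Given censoring of such deaths, the direction is certain: reported DoR is never shorter than under progression-or-death, and its curve is higher once any responder dies without documented progression. The size is not known. A factor of 1.05 to 1.43 rests on constant hazards and an assumed s of 5% to 30%; with no such deaths the two definitions agree. No error rate, power or sample size changes, and the primary safety analysis is untouched.

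**What to change.** In section 9.7.2, define DoR as the time from the first documented CR or PR to the first documented progression or death from any cause, whichever is first, and state that it follows the same censoring rules as PFS. Carry the same sentence into the SAP, before the interim report.

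No new data are needed: response, progression and death dates are already collected for ORR, PFS and OS. The only downside is that the reported DoR may be shorter.

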9.8. Quality Control

Syneos Health and Blueprint Medicines are responsible for following standard operating procedures (SOPs) to ensure data quality and integrity, including archiving of statistical programs, appropriate documentation of data cleaning and validity for created variables, and description of available data. All sites will be trained on the protocol, study logistics, and the electronic data capture (EDC) system. Investigators will be reminded of the processes and importance of reporting all AEs, SAEs, AESIs and other information.

The investigator is responsible for entering data in a timely manner and verifying that data are accurate and correct by physically or electronically signing the eCRF. The investigator must permit study-related monitoring, audits, institutional review board (IRB) review, and regulatory agency inspections and provide direct access to source data documents. On-line logic checks will be built into the EDC system as much as possible, so that missing or illogical data are not submitted. In the event that inconsistent data persist, queries may be issued electronically to the clinical study centre and answered electronically by that study centre's personnel.

9.9. Limitations of the Research Methods

9.9.1. Selection Bias

For patients who will be newly enrolled into this study, inviting consecutive patients at each site will reduce selection bias. In addition, AE rates obtained from this study will be compared with expected rates from the pooled analysis of AEs for all lines from the BLU-285-1101 and BLU-285-1303 trials. Survivor bias will be avoided (i.e. outcome ascertainment only for those who make it to the start of this study) by including patients who discontinued avapritinib treatment before enrolment in this study.

9.9.2. Information bias

Relying on investigators to fill out the assessment forms might induce the presence of missing data, which can result in bias. Entry of prospectively collected data in eCRFs will minimise missing or incorrect data by having automated queries. Clear instructions and engagement with the study staff with appropriate training will minimise the amount of missing data.

This study will collect both retrospective and prospective data. The retrospective data maybe of lesser quality than the prospective data that will be collected from enrolment, with more missing data and fewer details. It is therefore important to determine the impact of this in sensitivity analyses, and include rules about how missing data will be handled in the SAP. Also, if the data collected from the retrospectively enrolled patients is of poor quality or insufficient, the number of newly enrolled patients will be increased, if feasible.

9.9.3. Effect modifiers

Effect modification occurs when the effects of a treatment vary by presence/level of another factor (effect modifier). Stratified outcome analyses or analyses restricted to a selection of the study population will be conducted when deemed necessary and feasible, such as when population characteristics and results differ greatly between patients receiving their first dose in a controlled trial setting (i.e. enrolled in BLU-285-1101), a semi-real world setting (i.e. enrolled in a CUP or EAP and likely unable or ineligible to participate in BLU-285-1101) or real-world setting (i.e. receiving commercially available avapritinib as part of routine clinical care).

9.9.4. Site Selection Bias

After the feasibility assessment for sites to be included in this study, site selection bias will be reduced by taking a representative sample of sites when feasible given the number of sites per country. No sites will be prospectively excluded for reasons related to selection bias.

9.9.5. Patients Lost to Follow-up or With no Follow-up Data

Because the follow-up duration will be at least 24 months, the proportion of discontinued patients might be significant. As standard of care visits are assumed to take place every 2-3 months at least, this is expected to reduce loss to follow-up. Patients lost to follow-up will be compared with regard to baseline characteristics to patients with complete follow-up. Also, baseline characteristics will be compared between patients with no follow-up data (i.e. the EP) and the SP.

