9.1. Study design

This is a multinational, open-label, observational PASS that will evaluate the long-term safety and efficacy of avapritinib in the first line or following ≤ 4 months of imatinib treatment in at least 50 patients with PDGFRA D842V-mutated GIST. Three patient populations are planned to be enrolled:

- Patients with PDGFRA D842V-mutated GIST who are scheduled to receive avapritinib in the first-line (or have received imatinib for ≤4 months)
- Patients with PDGFRA D842V-mutated GIST who are already receiving treatment with avapritinib (in the first-line or following ≤ 4 months of imatinib treatment)
- Patients with PDGFRA D842V-mutated GIST who previously received treatment with avapritinib in the first line or following ≤4 months of imatinib treatment and have discontinued treatment

In addition to evaluating safety and efficacy of first-line avapritinib treatment, patients who were initially treated with imatinib for \leq 4 months are also being in included this study to allow for practical, real-world, clinical experience with use of avapritinib in the PDGFRA D842V-mutated GIST population setting and increase the feasibility of study completion in this ultra-rare patient population.

Informed consent will be obtained from all patients according to the regulatory and legal country-specific requirements of the participating site before enrolment in this study.

Patients who were scheduled to receive avapritinib prior to enrolment will initiate treatment after enrolment in this study based on the locally approved product label prescribing information. If a patient was already receiving avapritinib prior to enrolment, they will continue treatment at the same dose after enrolment. The dose level may be adjusted based on the locally approved product label prescribing information. Investigators must refer to the local prescribing information for contraindications, warnings and precautions as well as use in specific populations. As this study is observational, the decision to treat patients with avapritinib will be independent from the decision to enrol patients into the study.

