9.7.1. Analysis Populations

9.7.1.1. Enrolled Population (EP)

The enrolled population will consist of all patients who signed an informed consent.

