9.7.1.2. Safety Population (SP)

The SP will include all patients enrolled in the study who met the eligibility criteria and received at least one dose of avapritinib. The SP will be the primary analysis population for the efficacy and safety analyses.

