10. PROTECTION OF HUMAN SUBJECTS

10.1. Participant Information and Consent

The Investigator at each study center will ensure that the patient or his/her legally authorised representative is given full and adequate oral and written information about the nature, purpose, possible risk, and benefit of the study. Patients must also be notified that their participation is voluntary and that they are free to discontinue from the study at any time. The patient must be given the opportunity to ask questions and allowed time to consider the information provided.

Patients or their legally authorised representative will be required to sign a statement of informed consent that meets the requirements of 21 CFR 50, local regulations, ICH guidelines, HIPAA requirements, where applicable, and the IRB/IEC or study center. Remote consent by phone or mail may be considered where a patient is unable to meet with the investigator in person due to logistical or other reasons. For those patients that have discontinued avapritinib treatment and/or were lost to follow-up and consent cannot be obtained, the Investigator will consult their IRB/IEC for guidance on accessing these patients' data retrospectively.

The patient's signed and dated informed consent must be obtained before conducting any studyrelated procedures. The Investigator must maintain the original, signed consent form which includes the signature of the authorised person obtaining the informed consent. A copy of the signed form must be given to the patient.

The method of obtaining and documenting the informed consent and the contents of the consent will comply with ICH-GCP and all applicable regulatory requirement(s). The medical record must include a statement that written informed consent was obtained before the patient was enrolled in the study and the date the written consent was obtained.

Patients must be re-consented to the most current version of the ICF(s) during their participation in the study.

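### One of the two baseline comparisons in protocol section 9.9.5 labels patients without follow-up as the Enrolled Population, which contains essentially the whole Safety Population it is compared with

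*Protocol*

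**What the plan says.** Section 9.9.5 names two baseline comparisons to address incomplete follow-up.

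- The first reads "Patients lost to follow-up will be compared with regard to baseline characteristics to patients with complete follow-up".
- The second says that "baseline characteristics will be compared between patients with no follow-up data (i.e. the EP) and the SP".

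The two populations are fixed in section 9.7.1. For the EP: "The enrolled population will consist of all patients who signed an informed consent". For the SP: "The SP will include all patients enrolled in the study who met the eligibility criteria and received at least one dose of avapritinib".

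Section 9.1 adds the link between them: "Informed consent will be obtained from all patients according to the regulatory and legal country-specific requirements of the participating site before enrolment in this study". Section 10.1 and footnote d of Table 1 allow one possible exception, for patients who stopped avapritinib or were lost to follow-up. Where their "consent cannot be obtained, the Investigator will consult their IRB/IEC for guidance on accessing these patients' data retrospectively".

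The second comparison in 9.9.5 is the only place where the protocol puts the EP to use. Baseline characteristics, safety and efficacy are all summarised on the SP (sections 9.7.1.2 and 9.7.2).

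**The concern.** The parenthesis in 9.9.5 treats the EP as the group without follow-up data. By definition the EP is the widest group in the study, and it includes the SP patients with whom it is to be compared. A table of EP against SP will look balanced almost whatever the patients outside the SP are like, because most of the same people are counted on both sides.

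The SP definition raises a second difficulty. A patient who was dosed and then yields no further data is in the SP. Patients in the EP but outside the SP are those who were ineligible or never dosed. So neither the EP nor the part of it outside the SP is the group that the sentence describes.

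At stake is the credibility of one bias check. Section 9.1 lets patients enrol while only scheduled for avapritinib, so some consented patients may never be dosed. No other analysis in the protocol would show how they differ from those analysed.

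**Working it through.** The protocol gives no figure for this comparison, so there is nothing to reproduce. The check has two steps.

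**1. Membership of the groups**

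| Patient | In EP (9.7.1.1)? | In SP (9.7.1.2)? |
|---|---|---|
| Consented, eligible, dosed, has follow-up data | yes | yes |
| Consented, eligible, dosed, no follow-up data | yes | yes |
| Consented, never dosed | yes | no |
| Consented, not eligible | yes | no |
| Retrospective, no consent, data use permitted by the IRB/IEC | no | possibly |

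Apart from the last row, the SP lies inside the EP. Patients without follow-up data (row 2, and probably rows 3 and 4) are spread over both sides of the planned comparison.

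**2. How much of a real difference remains visible**

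Inputs:
- n_SP = 50. Section 9.5 plans at least 50 enrolled patients; using this as the SP size is an assumption.
- m = number of EP patients outside the SP. The protocol does not give it, so it is varied by assumption.
- The last row of the table is ignored.

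The EP mean is a weighted average:

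mean(EP) = [n_SP × mean(SP) + m × mean(outside)] / (n_SP + m)

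Subtracting mean(SP) gives

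mean(EP) − mean(SP) = [m / (n_SP + m)] × [mean(outside) − mean(SP)]

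The same identity holds for proportions. For an assumed true difference of 20 percentage points:

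| m (assumed) | Share visible | 20 points appear as |
|---|---|---|
| 3 | 3/53 = 5.7% | 1.1 points |
| 5 | 5/55 = 9.1% | 1.8 points |
| 10 | 10/60 = 16.7% | 3.3 points |
| 20 | 20/70 = 28.6% | 5.7 points |

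If 50 is instead the size of the EP, the shares are 3/50 = 6%, 5/50 = 10%, 10/50 = 20% and 20/50 = 40%. The picture is the same for small m. At least half of a true difference is hidden unless m exceeds n_SP.

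A worked case with assumed counts: 20 of 50 SP patients (40%) and 4 of 5 patients outside it (80%) have a given characteristic. Disjoint groups differ by 80% − 40% = 40 points. EP against SP gives 24/55 − 20/50 = 43.6% − 40.0% = 3.6 points, which is 9.1% of 40.

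**The case against.** **The main phrase is right and only the gloss is wrong.** The sentence and the section heading both speak of patients with no follow-up data. An analyst who follows that description and ignores the parenthesis would not tabulate the whole EP against the SP. This stands in part: the dilution arises only if the comparison is run as labelled. But the label names a defined analysis population, and programming from the definitions would follow it.

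**The excluded group may be tiny.** Two of the three groups in section 9.1 have already taken avapritinib, so they can fall outside the SP only through ineligibility. This stands. It makes the dilution stronger, but it also limits what a corrected comparison can show. With an age standard deviation of 12 years (an assumption, not in the protocol), 5 against 50 patients gives a standard error of 12 × √(1/5 + 1/50) = 5.6 years, or about ±11 years at 95%. The half-width is about ±14 years for 3 patients and ±8 for 10. The corrected check is therefore descriptive only.

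**The information is not lost.** If EP and SP are tabulated side by side with their numbers, counts for the excluded patients follow by subtraction (24 − 20 = 4 of 55 − 50 = 5 in the worked case). This is true, but the reader has to know to do it.

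**The SP is not strictly inside the EP.** Retrospective patients analysed without signed consent could be in the SP only. This is an edge case that leaves the overlap essentially intact.

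**A stronger reading.** A reader might infer that the protocol's whole check on attrition is reduced to almost nothing. The document does not support that. Comparing patients lost to follow-up with those completely followed uses disjoint groups, and the label does not touch it. How little remains of the second comparison depends on m, which is not stated.

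**Conclusion.** The second baseline comparison in section 9.9.5 contradicts the definitions in 9.7.1.1 and 9.7.1.2 and is mis-specified. Run as labelled, it retains about 6% to 29% of any true difference for 3 to 20 patients outside an SP of 50. Both the values of m and the SP size are assumptions. The direction does not depend on them: a real difference is always shrunk, so the table can suggest balance that it has no means of detecting.

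The consequence is limited. This is a descriptive check in the limitations section. It would be wrong to infer that adverse event rates, response rate or survival estimates are affected, since these are computed on the SP under either wording. Section 9.7 leaves missing-data handling to the SAP, but the protocol itself fixes both population definitions and this comparison, so the conflict belongs in the protocol. Severity: minor.

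**What to change.** Delete the parenthesis that equates the group with the EP, and specify disjoint groups. Removing the overlap alone is not enough: comparing the EP outside the SP with the full SP would leave dosed patients without follow-up in the reference group.

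Suggested content for the sentence: baseline characteristics of SP patients with follow-up data (the reference) will be tabulated beside those of

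- (a) EP patients not in the SP, by reason (not eligible, never dosed), and
- (b) SP patients with no post-baseline data, that is, nothing recorded after the baseline period of Table 1.

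Show the number in each group and present the results descriptively, because groups (a) and (b) will probably be small. If retrospective data are used without signed consent under IRB/IEC guidance, state to which population those patients belong. If the SAP repeats the sentence, correct it there as well.

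The cost is one sentence and one table layout. The data are those already planned, and no analysis population or estimate changes.
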